1. REPORTING & ANALYSIS PLAN SYNOPSIS

Overview	Key Elements of the RAP						
Purpose	The purpose of this Reporting and Analysis Plan (RAP) is to describe the planned summaries and statistical analyses to be included in the Clinical Study Report (CSR) for Protocol ARI114265.						
Protocol	
This RAP is based on the protocol amendment 04 (Republished) (Dated: 08/JUL/2014) of study ARI114265 [GSK Document No. : RM2010/00134/05]. This document contains the RAP amendment 01.
 
The aim of the study is to investigate whether combination therapy with dutasteride and tamsulosin is more effective than tamsulosin monotherapy for the improvement of symptoms and health outcomes in a population at increased risk of BPH clinical progression including older men (≥ 50 yrs), with moderate-severe symptoms of BPH, enlarged prostates (≥ 30 cc) and PSA ≥ 1.5 ng/mL.
						
Primary Objective	The primary objective is to assess the efficacy of combination treatment with dutasteride 0.5mg and tamsulosin 0.2mg once daily in providing superior symptomatic improvement in subjects with BPH compared with once daily tamsulosin 0.2mg monotherapy after 2 years of treatment.						
Primary Endpoint	The primary endpoint is change from baseline IPSS at Year 2 (Month 24 Visit); earlier timepoints (Month 21 \rightarrow Month 3) are considered secondary endpoints.						
Study Design	
This is a multicenter, randomized, double-blind, parallel group study. Eligible subjects will receive placebo tamsulosin and placebo dutasteride for four weeks in a single-blind, placebo, run-in period. Each subject will then be randomized to one of the following two treatment groups (1:1 ratio) for the double-blind phase (104 weeks) of the study:
 
 --Dutasteride 0.5mg once daily + tamsulosin 0.2mg once daily --Dutasteride placebo once daily + tamsulosin 0.2mg once daily 
Subjects will self-administer the study medication once daily for up to 104 weeks (2 years). Subjects will return to the clinic at 13 week intervals post-randomization during the 2 year treatment period (i.e. at 13, 26, 39, 52, 65, 78, 91, and 104 weeks).
						
Planned Analyses	
Within this RAP, the following additional references may be made for brevity:
 
  
 --Full Treatment Description--	--Short Treatment Descriptions--	
   
 Dutasteride 0.5mg once daily + tamsulosin 0.2mg once daily or	-Combination -Dut 0.5mg + Tam 0.2mg -Dut + Tam	
 
 Dutasteride placebo once daily + tamsulosin 0.2mg once daily	-Tamsulosin Monotherapy -Tam 0.2mg -Placebo + Tam 0.2mg -Tam	
  
 
The study population, efficacy, safety, and health outcomes summaries and analyses will be based on the Intent-to-Treat (ITT) population; few exceptions will be
	--Full Treatment Description--	--Short Treatment Descriptions--	Dutasteride 0.5mg once daily + tamsulosin 0.2mg once daily or	-Combination -Dut 0.5mg + Tam 0.2mg -Dut + Tam	Dutasteride placebo once daily + tamsulosin 0.2mg once daily	-Tamsulosin Monotherapy -Tam 0.2mg -Placebo + Tam 0.2mg -Tam
--Full Treatment Description--	--Short Treatment Descriptions--						
Dutasteride 0.5mg once daily + tamsulosin 0.2mg once daily or	-Combination -Dut 0.5mg + Tam 0.2mg -Dut + Tam						
Dutasteride placebo once daily + tamsulosin 0.2mg once daily	-Tamsulosin Monotherapy -Tam 0.2mg -Placebo + Tam 0.2mg -Tam						

Overview	Key Elements of the RAP
	
noted within the RAP. Summaries and analyses are defined within this RAP. The following are high level summary and analyses types.
 
 • Study population summaries will be presented overall and by treatment group and will include accountability, disposition, demographic characteristics, baseline characteristics, protocol deviations, and concomitant medications. • The primary efficacy analyses and treatment group comparisons will be in terms of IPSS change from baseline. • Secondary efficacy analyses and treatment group comparisons will be in terms of prostate volume, Qmax, IPSS improvement levels (≥ 2 points, ≥ 3 points, $\geq 25\%$), Qmax improvement levels (≥ 3 ml/sec, $\geq 30\%$), and time to AUR or BPH-related surgery. • Safety summaries will be presented by treatment group and will be in terms of study drug exposure, adverse events, clinical laboratory evaluations, serum PSA, post void residual volume, qualitative breast examination, digital rectal examination, vital signs, and suicidality assessment using C-SSRS. • Health Outcomes analyses and treatment group comparisons will be in terms of BPH-Related Health Status (IPSS Question 8), BPH Impact Index, and Problem Assessment Scale of the Sexual Function Inventory (PAS SFI).
Analysis Populations	
 • The ITT Population is comprised of all randomized subjects regardless of whether or not treatment was administered. • The Per-Protocol (PP) Population is comprised of all ITT subjects who comply closely with the protocol. Specifically this includes ITT subjects who do not have a deviation which requires exclusion from the PP population. The PP population will not be analyzed if this population comprises more than 80% of the ITT population.
Hypothesis	
The primary endpoint is change from baseline IPSS at Year 2. Let the following represent the mean change from baseline IPSS for each treatment group:
 
$H_{dut+tam}$: Combination (dutasteride 0.5mg and tamsulosin 0.2mg) treatment group H_{tam}: Tamsulosin (tamsulosin 0.2mg treatment group)
 
Then the primary null and alternative hypotheses to be tested at Year 2 are as follows:
 
Null Hypothesis: $H_{dut+tam} = H_{tam}$ Alternative Hypothesis: $H_{dut+tam} \neq H_{tam}$
 
Two-sided tests of the null hypothesis will be conducted at the 0.05 level of significance to show superiority of the combination treatment group compared to tamsulosin 0.2mg at 2 years of treatment.

Primary Analyses	The primary efficacy parameter after two years of study treatment is change from baseline IPSS. Change in IPSS from baseline will be compared at each scheduled post-baseline visit for combination treatment versus tamsulosin 0.2mg using a general linear model with effects for treatment, cluster, and baseline IPSS.
Secondary	Secondary efficacy analyses will be in terms of prostate volume, Qmax, IPSS

Overview	Key Elements of the RAP
Analyses	improvement levels, Qmax improvement levels, and time to AUR or BPH-related surgery using appropriate statistical methodology defined within this RAP.

2. SUMMARY OF KEY PROTOCOL INFORMATION

2.1. Changes to the Protocol Defined Statistical Analysis Plan

There were no changes or deviations to the originally planned statistical analysis specified in the ARI114265 protocol amendment 04 (Republished) (Dated 08/JUL/2014).

This document contains the RAP amendment 01 which is based on the protocol amendment 04 noted above. RAP amendment 01 revisions primarily include programming and reporting clarifications, limited expansion of efficacy subgroup summaries, and limited expansion of supporting analyses for secondary endpoints. This amendment 01 includes no major changes to the planned analyses. The summary of RAP amendment 01 changes is contained in [Appendix 17](#).

2.2. Study Objective(s) and Endpoint(s)

Objectives	Endpoints
Primary Objectives	Primary Endpoints

 To assess the efficacy of combination treatment with dutasteride 0.5mg and tamsulosin 0.2mg once daily in providing superior symptomatic improvement in subjects with BPH compared with once daily tamsulosin 0.2mg monotherapy after 2 years of treatment 	
 Change in IPSS from baseline at Year 2.
Secondary Objectives	Secondary Endpoints

 To assess efficacy and safety of combination treatment with dutasteride 0.5mg and tamsulosin 0.2mg including the clinical outcomes of AUR or BPH-related prostatic surgery compared with tamsulosin 0.2mg monotherapy after 2 years of treatment. 	
Efficacy
 
 Percent change in prostate volume from baseline Proportion of subjects with IPSS improvement of ≥ 2 points and ≥ 3 points from baseline and, separately, $\geq 25\%$ improvement from baseline Change in Qmax from baseline Proportion of subjects with Qmax improvement of $\geq 3\text{mL/sec}$ and, separately, $\geq 30\%$ improvement from baseline Time to event/ proportion of subjects with AUR or BPH related prostatic surgery Time to event/proportion of subjects with AUR Time to event/proportion of subjects undergoing BPH related prostatic surgery 
Health Outcome Measures
 
 Change in BPH-Related Health Status (Q8 of IPSS) from Baseline Change in BPH Impact Index (BII) from Baseline

Objectives	Endpoints
	
 Change in Problem Assessment Scale of the Sexual Function Inventory (PAS-SFI), from Baseline Resource Use related to AUR and BPH-related surgical events. 
Safety
 
 Adverse Events Change in total serum PSA from baseline Vital signs Post-void residual volume Clinical laboratory measurements (including haematology, chemistry) Physical examination: digital rectal examination (DRE) and qualitative breast examination Suicidality (C-SSRS)
Exploratory Objectives	Exploratory Endpoints

 Pharmacogenetics (PGx) Research Note: PGx planned summaries and analyses will be documented outside this RAP. 	
 Relationships between genetic variants in DNA from patient blood and any unexplained or unexpected response to treatment (as monitored by safety, tolerability, and efficacy parameters) that may have an underlying genetic mechanism.

 Population Pharmacokinetics (PPK) Research Note: PPK planned summaries and analyses will be documented outside this RAP 	
 Characterization of PPK of dutasteride when given in combination with tamsulosin to Chinese men with BPH.

2.3. Study Design

Overview of Study Design and Key Features	
Design Features	
 • Multicenter within 4 countries: China, Japan, Korea, and Taiwan. • Randomized, double-blind, parallel group study to assess the efficacy of combination treatment with dutasteride 0.5mg and tamsulosin 0.2mg once daily in providing superior symptomatic improvement in subjects with BPH compared with once daily tamsulosin 0.2mg monotherapy after 2 years of treatment.
Dosing / Treatment Assignment	
 • Placebo tamsulosin and placebo dutasteride for four weeks in a single-blind, placebo, run-in period. • Thereafter randomized to one of the following two treatment groups (1:1 ratio) for the double-blind phase (104 weeks) of the study: 
 --Dutasteride 0.5mg once daily + tamsulosin 0.2mg once daily or --Dutasteride placebo once daily + tamsulosin 0.2mg once daily.
Interim Analysis	No interim analyses are planned for this study.

2.4. Statistical Hypotheses

The primary endpoint is change from baseline IPSS. Let the following represent the mean change from baseline IPSS for each treatment group:

$H_{dut+tam}$: Combination (dutasteride 0.5mg and tamsulosin 0.2mg) treatment group

H_{tam} : Tamsulosin 0.2mg treatment group

Then the primary null and alternative hypotheses to be tested at Year 2 are as follows:

Description	Null Hypothesis	Alternative Hypothesis
Combination versus tamsulosin 0.2mg	$H_{dut+tam} = H_{tam}$	$H_{dut+tam} \neq H_{tam}$

Two-sided tests of the null hypothesis will be conducted at the 0.05 level of significance to show superiority of the combination treatment group compared to tamsulosin 0.2mg at 2 years of treatment.

3. PLANNED ANALYSES

3.1. Interim Analyses

No interim analyses are planned for this study.

3.2. Final Analysis

The planned primary analyses will be performed after completion of the following sequential steps:

1. All subjects have completed the 104-week study treatment period study as defined in the protocol.
2. All required database cleaning activities have been completed and primary database release and primary database freeze have been declared by Data Management. Reference 'primary database' description below.
3. All criteria for unblinding the randomization codes have been met.
4. Randomization codes have been distributed according to RandAll NG procedures.

The primary database freeze, using standard Data Management practices, will occur after the last subject completes the 104-week randomized treatment phase. Statistical analysis and reporting in support of international regulatory submissions will be in terms of this primary database freeze and will be referred to as the 'Final Analysis' or primary 'Statistical Analysis Complete' (SAC). Reference Section 9, Country-Specific Summaries and Analyses, for a description of a secondary country-based statistical analysis complete package.

3.3. Targeted Follow-Up Questionnaire (TFUQ) Report

As documented in protocol and elsewhere in this RAP, this study includes a Targeted Follow-Up Questionnaire (TFUQ) for subjects with sexual function related adverse events leading to study withdrawal. Using the TfuQ, subjects will be followed for up to 6 months after the last dose of study drug. It is anticipated that the final TfuQ data component will be included in the above referenced primary database freeze.

However, if there are ongoing TfuQs at the time of primary database freeze, and anticipated follow-up and receipt of these data would create a delay in analyzing and reporting the study results then the primary freeze may occur with exclusion of outstanding TfuQ data. Thereafter, a secondary database freeze will occur in terms of newly finalized and recorded TfuQ data (since primary freeze). The decision to perform a secondary freeze will be made soon after last subject last visit milestone by Project Team with input from Data Management, International Regulatory Affairs, Clinical Statistics, Clinical Development, and Clinical Operations. This secondary freeze will be in terms of datasets containing the actual TfuQ and as well as any TfuQ-related datasets. Only TfuQ-related tabular summaries and listings (related to newly frozen datasets) will be updated with the secondary freeze. TfuQ-related summaries and listings for this secondary freeze will be referred to as 'TfuQ Report'.

4. ANALYSIS POPULATIONS

Analysis populations are defined in the following table.

Population	Definition / Criteria	Analyses Evaluated
Intent-To-Treat (ITT)	
 Comprised of all randomized subjects regardless of whether or not treatment was administered This population will be based on the treatment to which the subject was randomized. Any subject who receives a treatment randomization number will be considered to have been randomized. 	
 All.
Per-Protocol (PP)	
 Comprised of all ITT subjects who comply closely with the protocol. Specifically this includes ITT subjects who do not have a deviation which requires exclusion from the PP population. Protocol deviations that would exclude subjects from the PP population are defined in Section 4.1.3 (Deviations which Require Exclusion from the Per-Protocol Population) and Appendix 1 (Exclusions from the Per-Protocol Population). The PP population will not be analyzed if this population comprises more than 80% of the ITT population. 	
 Primary efficacy endpoint only if this population comprises 80% or less of the ITT Population. Details on specific summaries and analyses are outlined in Section 7, Primary Statistical Analyses.

NOTES :

- 'All Enrolled Subjects' is referenced in at least one tabular summary. Enrolled subjects include those who entered placebo run-in phase and/or who were randomized.

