Please refer to [Appendix 1](#): Exclusions from the Per-Protocol Population for details on sources and processing these deviations.

Deviations which require exclusion from the Per-Protocol population will be summarized and listed. The Per-Protocol deviations tabular summary will be in terms of number and percent of subjects with any deviation and for each deviation. Summaries will be output by each of the two randomized treatment groups and overall.

4.1.4. Deviations which Require Exclusion from the Per-Protocol Population but not Tracked or Identified as Important by Study Team

For brevity, in this section ‘deviations which require exclusion from the per-protocol population’, defined in Section [4.1.3](#), will be referred to as ‘Per-Protocol Deviations’. In accordance with SOP-130050 and as clarified in GUI-315049, Per-Protocol Deviations are a subset of Important Protocol Deviations. As described in [Appendix 1](#), some Per-Protocol Deviations may be identified programmatically and/or some may be identified post database freeze and unblinding. Therefore, it is not feasible to manually enter all Per-Protocol Deviations to the Study Team spreadsheet (referenced in Section [4.1.2](#)) and thus not all Per-Protocol Deviations will be tracked or identified as Important by Study Team.

Per-Protocol Deviations which were not tracked or identified as Important by Study Team will be reported in 1) Listing of Important Deviations and flagged as such, and 2) Summary of Important Protocol Deviations.

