7. PRIMARY STATISTICAL ANALYSES

7.1. Primary Efficacy Analyses

7.1.1. Overview of Planned Primary Efficacy Analyses

The primary efficacy parameter after the 2nd year of the study is change from baseline IPSS (International Prostate Symptom Score). The IPSS questionnaire consists of seven questions with each question score ranging from 0 to 5. It is administered at screening, baseline, and at each of the scheduled post-baseline treatment phase visits.

IPSS (also called IPSS total score) is the sum of the seven questions. IPSS summaries and analyses will be in terms of the total (score); exceptions will be noted such as for supporting summaries of individual questions. For calculation of the IPSS total, missing individual responses will be imputed when at least four of the seven questions are answered (nonmissing). For the imputation, the average of the nonmissing responses will be calculated and rounded to the nearest integer. This average will be imputed for the original missing response(s). If at least 20% of the subjects have at least one imputed IPSS then the statistical analyses will be repeated based on non-imputed scores.

The efficacy analyses will be based on the Intent-to-Treat (ITT) population. [Table 3](#) provides an overview of the planned IPSS summaries and primary efficacy analyses. A list of planned data displays is in [Appendix 15](#): List of Data Displays.

Table 3 Overview of Planned Primary Efficacy Analyses

Endpoint	Absolute			Change from Baseline			% Change from Baseline		
	L	F	T	L	F	T	L	F	T
IPSS (International Prostate Symptom Score) Change from Baseline									
Primary Analysis (Month 24 Visit)	Y ^[1]			Y	Y ^[1]	Y	Y ^[2]		
Supporting and Sensitivity Analyses of Primary Endpoint									
Mixed-Model Repeated-Measures (MMRM) Analysis (At Visit)						Y			
IPSS Change from Baseline by Subgroup ^[3]						Y			
Individual IPSS Questions	Y ^[1]		Y			Y			
IPSS Percentage Change from Baseline							Y ^[1]		Y
IPSS Non-imputed Score Analysis ^[4]			Y		Y	Y			
IPSS Per-Protocol Population Analysis ^[5]			Y		Y	Y			

NOTES :

- T = Table, F = Figure, L = Listing, Y = Yes display generated. All outputs are based on ITT population except [4].
- Tables and figures have separate outputs for LOCF and At Visit, except for baseline summaries.
- 1. Individual questions 1 – 7 responses, total score, total score change from baseline, and percentage change from baseline are combined in a single listing and presented for every visit.

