7.1.3. Supporting and Sensitivity Analyses of Primary Endpoint

The following describes supporting and sensitivity analyses of the primary endpoint.

Mixed-Model Repeated-Measures (MMRM) Analysis: As a supportive analysis, IPSS will be analyzed using a mixed-model repeated-measures (MMRM) analysis including ITT population data from the scheduled post-baseline assessments. Details are provided in [Appendix 13](#), Mixed-Model Repeated-Measures Analysis.

IPSS Change from Baseline by Subgroup: For each subgroup, IPSS change from baseline summaries will be output by treatment group at Month 12 and at Month 24 for the ITT population using both LOCF and At Visit approaches. No statistical testing will be performed. Subgroups are defined in [Appendix 10](#), Examination of Covariates and Subgroups.

Individual IPSS Questions 1 – 7: Each of the 7 IPSS individual question responses will be summarized at Baseline, Month 12, and Month 24 by treatment group. Month 12 and Month 24 change from baseline will be summarized by treatment group for each of the 7 questions. The summaries will be based on the ITT population and presented using both LOCF and At Visit approaches. No statistical testing will be performed.

IPSS Percentage Change from Baseline: Percentage change from baseline is defined in [Appendix 6](#). IPSS percentage change from baseline will be summarized by treatment group at each scheduled post-baseline assessment. The summaries will be based on the ITT population and presented using both LOCF and At Visit approaches. No statistical testing will be performed.

IPSS Non-Imputed Score Analysis: IPSS missing response imputation procedure is described above. If at least 20% of the ITT subjects have at least one imputed IPSS then the tables, figures, and analyses described in Section 7.1.2 (Planned Primary Efficacy Statistical Analyses) will be repeated using non-imputed scores.

IPSS Per-Protocol Population Analysis: Per-Protocol (PP) population is defined in Section 4. If the PP population comprises 80% or less of the ITT population, then the tables, figures, and analyses described in Section 7.1.2 (Planned Primary Efficacy Statistical Analyses) will be repeated using the PP population.

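### The triggers for the Per-Protocol analysis and the non-imputed IPSS repeat are pooled over both arms, so a supportive check can be skipped by rule when the arms differ

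*SAP*

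**What the plan says.** Two supportive analyses of the primary endpoint are conditional.

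- **Per-Protocol analysis.** Section 4 states "The PP population will not be analyzed if this population comprises more than 80% of the ITT population", and the same table lists the PP analysis as "Primary efficacy endpoint only if this population comprises 80% or less of the ITT Population". Section 1 carries the same 80% rule. Section 7.1.3 opens the PP analysis with "If the PP population comprises 80% or less of the ITT population". The denominator is the ITT population, defined in Section 4 as "Comprised of all randomized subjects regardless of whether or not treatment was administered", so it covers both arms together.
- **Non-imputed IPSS analysis.** Section 7.1.1 says "If at least 20% of the subjects have at least one imputed IPSS then the statistical analyses will be repeated based on non-imputed scores". Section 7.1.3 gives the condition as "If at least 20% of the ITT subjects have at least one imputed IPSS".

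Neither rule has a by-arm condition. On reporting, Section 4.1.3 says of the deviations that exclude men from PP: "Summaries will be output by each of the two randomized treatment groups and overall" (Table 1.9). Table 2.1 summarises IPSS imputations; the list of displays does not say whether it is laid out by arm. Sections 8.3.1 and 8.3.3 use the same 20% rule for the BII and PAS SFI totals.

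**The concern.** ITT and PP estimates can separate when exclusions differ between arms. Several of the 19 excluding deviations in Section 4.1.3 can arise after randomization and could depend on treatment: compliance below 75% or above 125% (04, 05), and phytotherapy, alpha-blockers or other prohibited therapy during the study (14, 15, 18). A fraction pooled over arms responds to the average of the two rates and not to the difference between them. The same holds for item imputation.

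The by-arm deviation table would show an imbalance, but the plan attaches no action to it. In contrast, Appendix 7 (Section 11.7.2.2) commits to further analysis if LOCF and At Visit results disagree. A PP or non-imputed analysis added after someone has read the by-arm table would be post hoc, which is what a pre-specified rule should avoid.

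**Working it through.** The SAP states no figure on this point, so there is nothing to reproduce. The check is arithmetic on the stated rules.

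**Inputs**
- PP analysis run if PP/ITT is 80% or less (Sections 1, 4, 7.1.3).
- Non-imputed repeat run if at least 20% have an imputed IPSS (Sections 7.1.1, 7.1.3).
- Allocation 1:1 (Section 1).
- Men per arm, n: not given in the SAP. Assumed range 100 to 500; it affects only rounding.

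**Formula.** Let a and b be the two arm rates, either of exclusion from PP or of having an imputed IPSS. With equal arms the pooled rate is (a + b)/2.
- PP analysis skipped if 1 − (a + b)/2 > 0.80, that is, a + b < 0.40.
- Non-imputed repeat skipped if (a + b)/2 < 0.20, that is, a + b < 0.40.

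**Examples**
- Exclusions of 30% and 8%: PP/ITT = 1 − 0.38/2 = 81%. Skipped.
- Exclusions of 25% and 10%: PP/ITT = 1 − 0.35/2 = 82.5%. Skipped.
- Imputed IPSS in 30% and 8%: pooled 0.38/2 = 19%. Skipped.

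**Boundary.** At exactly 40% and 0%, PP/ITT = 80% and the pooled imputed share is 20%. Both cut-offs include their boundary, so both checks are run. The ceiling is therefore just under 40%, and only if the other arm has none:

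| n per arm | Most men in one arm, none in the other, check still skipped |
|---|---|
| 100 | 39 (39.0%) |
| 200 | 79 (39.5%) |
| 300 | 119 (39.7%) |
| 400 | 159 (39.75%) |
| 500 | 199 (39.8%) |

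**Effect of the other arm.** The ceiling is 40% minus the other arm's rate, and falls point for point:

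| Other arm | One-arm ceiling (just under) |
|---|---|
| 2% | 38% |
| 5% | 35% |
| 10% | 30% |
| 15% | 25% |

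**Unequal realised split.** If an arm holds share w of the men and the other arm has none, its ceiling is 0.20/w: 0.20/0.48 = 41.7% for the smaller arm of a 48:52 split, and 0.20/0.52 = 38.5% for the larger.

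**Cut-off applied to each arm.** The check is then skipped only if a < 0.20 and b < 0.20. That implies a + b < 0.40, so a by-arm rule runs the check in every case where the pooled rule does, and in more. The largest unexamined one-arm share falls from just under 40% to just under 20%.

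**The case against.** The case against giving this much weight is substantial.

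- **The primary result does not depend on it.** The trial tests superiority on ITT, and PP is only supportive. The At Visit analysis, the MMRM (Appendix 13) and the residual and interaction checks (Appendix 12) run regardless. This stands. However, the planned At Visit and MMRM analyses use the ITT men and the item-imputed totals, so they do not replace either conditional check.
- **A large split is unlikely.** The trial is double-blind, and deviations 01 and 06 to 11 concern run-in or eligibility, so they can differ by arm only by chance. This stands for the extreme case. Moderate splits such as 25% against 10% need no such assumption.
- **A by-arm fraction is also an imperfect detector.** Equal rates for different reasons can separate ITT from PP, and unequal rates need not. This stands, and it favours running the checks always.
- **A by-arm rule needs treatment codes.** Appendix 1 wants deviations identified before unblinding where possible. But Section 4.1.4 and Appendix 1 accept that some PP exclusions are settled only after unblinding, so this is no real obstacle.

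A reader might also infer that counting an imputed IPSS at any visit is a fault. It is not: it makes the trigger fire more readily. It also fits an analysis that covers every post-baseline visit and carries earlier totals forward under LOCF.

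**Conclusion.** The point holds as a minor weakness. Both triggers are pooled, and under 1:1 allocation each check is skipped whenever the arm rates sum to less than 40%, however unequal they are. The result rests on the stated cut-offs and on equal arms; sample size changes only the rounding.

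Three stronger readings are not supported:
- One arm cannot have a full 40% affected with the check unrun under equal allocation. At 40% against none both checks are run.
- Men with imputed items are not lost. They stay in the ITT analysis.
- A PP imbalance would not be hidden, because deviations are tabulated by arm.

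Nothing in the SAP allows an effect on the IPSS treatment difference to be calculated, and none is claimed.

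**What to change.** In Sections 1, 4 and 7.1.3 (PP) and 7.1.1 and 7.1.3 (IPSS), do one of the following:

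1. **Preferred:** delete the conditions and always run the PP and non-imputed IPSS analyses. This needs no treatment codes to decide whether to run them.
2. **Alternative:** keep each cut-off but apply it in either treatment group.

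Change Sections 7.1.1 and 7.1.3 together so that the two statements of the IPSS trigger still agree. If a trigger is kept, leave it counting an imputed IPSS at any visit. Narrowing it to baseline or Month 24 would be ambiguous under LOCF and could miss carried-forward totals. Make the same change to the 20% rule in Sections 8.3.1 (BII) and 8.3.3 (PAS SFI).

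The cost is a phrase in each section and at most one extra set of outputs per check, from programs already needed for the main analyses. If Section 9 is taken to cover these outputs, they would also be repeated by country.
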